Objectives	In patients at risk identified by FINDRISC (i.e., score greater than or equal to 12), determine the difference in the number of patients who attend a confirmatory test (GTT) after the isolated application of the screening questionnaire versus the completion of the supplemented questionnaire by POC-A1c.
Study design	Prospective, open label, randomized, controlled study.
Population	Adult patients with no known diagnosis of diabetes
Inclusion criteria	
 • Adult, aged over or equal to 18 years and less than or equal to 75 years. • Understand, accept, and sign informed consent • FINDRISC greater than or equal to 12
Exclusion criteria	
 • Previous diagnosis of type 1 or type 2 diabetes mellitus • Pregnancy or lactation at the time of inclusion in the study (referred by the subject). • History of cancer in the subject (must be in remission for 5 years) • Known history of familial hyperlipidemia. • Chronic use of systemic corticosteroids (Defined as: a dose greater than 5 mg of oral prednisolone or its equivalent and / or consumption greater than one month thereof). • Known history of hemophilia or other bleeding disorders • Known history of stage IV or V chronic kidney disease • Known history of HIV (on antiretroviral therapy) • History of sickle cell disease • Known history of glucose 6 phosphate dehydrogenase deficiency • Known history of blood transfusion in the past 3 months • Known history of erythropoietin therapy in the past 6 months.
Duration of the study	Each subject will participate in the study approximately 4 months, in addition, each patient will be given a follow-up call 30 days and 90 days from the date of inclusion in the study.

	
Comparative effectiveness of point-of-care glycosylated hemoglobin measurement (POC-A1c), vs. the current standard based on oral glucose tolerance test, for the early detection of Type 2 Diabetes Mellitus (T2DM) in Colombia. EDDIT-1 STUDY
	
Version: 3.0 Date: February 15, 2022

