- Describe the causes of non-performance of the confirmatory test and identification of predictors of non-performance or postponement of the diagnostic test within a maximum period of 90 days from the initial recommendation.

Study design

Overview

Study, prospective, open, randomized, controlled.

Justification of the main elements of the protocol

The FINDRISC screening questionnaire has been previously studied and validated, can be applied quickly, economically and its low complexity makes them widely available (5,10). Similarly, previous studies have shown that periodontal disease is related to the appearance of alterations in the glycemic profile so that up to 30% of adults over 30 years of age who attend general dentistry consultations are identified as a population at risk (3).

Despite the drawbacks to its mass application, OGTT remains included within the current CPGs and continues to be a reference test for the diagnosis of patients with DM2 (3).

Measurement of A1c may be more convenient than OGTT, particularly if performed at the point of care (POC-A1c). Additionally, the characteristics for its implementation and its technical profile are clearly established. However, its impact on the screening algorithm under real conditions of use is unknown and its profile for inclusion within a mass screening system has not yet been established.

Setting the primary endpoint

While it is possible to perform screening using any of the validated questionnaires, in real conditions of their implementation a second visit of the patient is required to perform a confirmatory test (GTT) and the loss to follow-up is required a major challenge for health systems. It is proposed that the implementation of POC-A1c can contribute to improving the follow-up rate in the context of population screening and facilitate the successful implementation of large-scale screening campaigns.

Therefore, the primary outcome is the probability of going to OGTT according to the strategy implemented.

Choice of comparator

Currently, the screening guidelines contemplate the completion of the FINDRISC questionnaire followed by a confirmatory test carried out in the centralized laboratory. Because of this, the recommended practice is established as a comparator.

Type of design

Prospective, open label, randomized, controlled study in adults with no known diagnosis of diabetes.

Study procedures

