A Pre-Screening activity will be carried out, with prior authorization of use of personal data, where the FINDRISC test will be applied to different population groups and in case the subjects obtain 12 points or more, they will be invited to participate in the study. Otherwise, participants with 11 points or less according to the application of FINDRISC will receive brief information on healthy lifestyles according to their risk group, ending the activity.

Once the Pre-Screening activity has been carried out, to carry out each day, a work site will be installed in the different places established to carry out the screening of the disease that will be attended by a doctor, bacteriologist, and nursing assistant. Subjects at risk identified by FINDRISC will be explained what the study consists of; if they wish to participate in it, and understand, accept, and sign the informed consent: the doctor will proceed to record the relevant data in their medical record, evaluate inclusion and exclusion criteria.

Subsequently, the participants will be randomized into 2 groups. Participants in group A (intervention) will be offered information on healthy lifestyles according to their outcome and will be given a measurement of POC-A1c*. In the participants of group B (control) they will be offered the same information on healthy lifestyles according to their FINDRISC result.

**The work site will have a properly covered cubicle, in which a POC-A1c equipment will be available with the necessary requirements of location and operation to guarantee the validity of the test. In this cubicle will be a laboratory assistant who executes the pre-analytical and post-analytical phase.*

In addition, all randomized participants will be invited to perform a GPOT in the CAIMED partner laboratory or in the laboratory of their choice with the preparation recommendations necessary for the realization of the same. For this purpose, they will be given an order that includes the date of screening, a tracking number and time window in which they must go (i.e., 30 days and with a second attempt-maximum window to 90 days).

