After 30 days from the application of the screening, a call will be made to the randomized subjects to check if they performed the indicated diagnostic test and the result of the OGTT, if the examination has been carried out, must be sent to the center (either by scanning, photographing, or bringing it to the research center). Otherwise, the causes of non-realization of the same will be investigated and a new call will be made after 90 days. In patients who, if they attended the performance of the OGTT and obtained a presumptive result of diabetes, a closing call will be made 30 days after the test was performed to confirm if they began control of their disease. For this, you will be instructed to attend a consultation by general medicine according to what is contemplated by your entity administering benefit plans, ending the follow-up.

Study population

Adult patients with no known diagnosis of diabetes attending a health care facility.

Inclusion criteria

- Adult, aged 18 years or older and under or equal to 75 years old
- Understand, accept, and sign informed consent
- FINDRISC greater than or equal to 12

Exclusion criteria

- Previous diagnosis of type 1 or type 2 diabetes mellitus
- Pregnancy or lactation at the time of inclusion in the study (referred by the subject)
- History of cancer in the subject (must be in remission for 5 years)
- Known history of familial hyperlipidemia
- Chronic use of systemic corticosteroids (Defined as: a dose greater than 5 mg of oral prednisolone or its equivalent and/or consumption greater than one month thereof).
- Known history of hemophilia or other bleeding disorders
- Known history of stage IV or V chronic kidney disease
- Known history of HIV
- Known history of sickle cell disease
- Known history of 6 phosphate dehydrogenase deficiency
- Known history of blood transfusion in the past 3 months
- Known history of erythropoietin therapy in the past 6 months.

Criteria and procedures for the withdrawal or suspension of subjects

Type and time of data collection corresponding to withdrawn subjects

The subject who decides to participate in the study can choose to withdraw at any time, since no therapeutic interventions are being applied, only guidance will be offered to the subject regarding their risk condition as has been established until that moment of the study and the moment in that its follow-up is terminated.

Whether to replace subjects and how

Withdrawn subjects will not be replaced.

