Follow-up of withdrawn subjects

Once the subject expresses his intention to withdraw, the follow-up will be terminated.

Criteria for the interruption of the study.

Since the intervention is not therapeutic and the technical conditions for performing laboratory tests are standardized, no a priori termination criteria are established.

Interventions

Description of interventions

The FINDRISC (applied in Pre-Screening activity) will be verified; for this it is necessary to take anthropometrics well as non-invasive measurements. Additionally, to establish the diagnosis of prediabetes or undiagnosed diabetes, invasive activities such as blood sampling are required.

Non-invasive measurements

Body weight (at 0.1 g precision) in lightweight underwear, without footwear, will be recorded at the screening visit as well as height (at 0.5 cm precision), that is, both measurements will be obtained at the beginning of the study. The waist and hip circumference will be taken twice, then the average of both measurements will be made.

Biochemical measurements

The PGTT will be carried out according to the standards of the allied laboratory or of preference by the patient, and under the local regulations of the country with the recommendations of the WHO. Ideally, the loading solution should contain 75 g of anhydride glucose and 1.6 g of citric acid, the first sample of glycemia will be obtained after 8 - 12 hours of fasting and the second sample will be obtained 2 hours after glucose loading. All this according to the recommendations described by the WHO.

PoC-A1c will be measured at the screening site using validated equipment that complies with international standards. Kits and processing methods will be ensured to be certified by the NGSP and standardized with the DCCT assay. The POC-A1c test shall be considered impaired for any value equal to or greater than 5.7% (3).

Enumeration of the participant

The enumeration of patients will be sequential since it is performed in a single center.

Allocation of the intervention

Once the participant has accepted and signed the informed consent, the doctor will verify the FINDRISC questionnaire previously applied in prescreening activities), as well as inclusion and exclusion criteria and random assignment will be carried out by the research team.

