The random allocation sequence will be automatically generated through the platform intended for this purpose. A member of the research team will record the group to which the participant was assigned on the data logging platform.

Instructions to the patient

In Pre-Screening activities, a member of the research team must give the participant a flyer with educational information about healthy lifestyles, regardless of the participant's score. In addition to all participants who enter the study, they will be given an order for the realization of the PWG with the relevant indications for the taking of the sample and the flyer mentioned above.

In this documentation must be the sequence number that was assigned to the patient, as well as their identification number so that when they go to the sampling site (CAIMED allied laboratory/Laboratory of their preference) they are identified as a participant in the study. This will make it possible to monitor which participants have already completed the GGP. 30 days after applying the screening questionnaire or the completion of the GTT, the follow-up call is made.

The script is as follows:

"Good morning / good afternoon / good evening, Madam/Sir (name of the subject). My name is (Contributor Name) I am (Position) We are calling you on behalf of the diabetes early detection study. As you recall, on the day (date

	
Effectiveness comparison of the hemoglobin measurement glycosylated at the point of care (POC-A1c), vs the standard current based on tolerance test oral to glucose, for the detection early of Diabetes Mellitus guy 2 (DM2) in Colombia. EDDIT-1 STUDY
	
Version: 3.0 Date: February 15, 2022

---	--	---

of inclusion in the study) you participated in the site (inclusion site to the study) in the diabetes study. I would like to know if you had the sugar test indicated by the doctor (corresponding to the day of completion of window 1 for the OGTT).

(Wait for a reply)

If the patient replies that the test was performed, the date and result should be confirmed and ask: "Could you please send us a photo or any proof of the report? Finally, the call should end like this: "Thank you very much Ms./Mr. (name of the subject). Remember to consult your doctor or your EPS to initiate timely management of the disease (in case it is impaired) or monitor the risk at least annually."

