If the answer is I have not taken the test: Could you please tell us why you have not taken the sugar test? Wait for a response, and document it, end the call like this: "Remember that we will call you in 2 months again to confirm if the test was done."

**The answers are recorded by the platform and will be analyzed qualitatively by the researchers.*

Scheduling of study visits (schedule)

Responsible	Prescreening	Visit 1	Phone Call 1 (30 days ± 3 days)	Phone Call 2 (90 days ± 3 days)	Phone Call 3 (30 days after reporting to the center ± 3 days, if applicable)
Doctor Bacteriologist Research Assistant	– Conferences of application of FindRisc as risk screening				
Doctor		Explanation of the study, its procedures and obtaining the consent informed. Review of eligibility criteria.			
Research Assistant		VERIFICATION of FINDRISC, Randomization and data processing on the platform			
Research Assistant		Data processing on the platform to the corresponding group			
Laboratory		Implementation of POC-A1c			

Effectiveness comparison of the hemoglobin measurement glycosylated at the point of care (POC-A1c), vs the standard current based on tolerance test oral to glucose, for the detection early of Diabetes Mellitus guy 2 (DM2) in Colombia. **EDDIT-1 STUDY**

Version: 3.0
Date: February 15, 2022

CRS			Follow-up call 30 days after the PGT request.	Follow-up call - 30-90 days after admission to the study in patients not attending OGTT.	Verification call 30 days from the report of the result of the requested test. To those who present an impaired OGMP and have requested a control doctor.

Bias Control

- **Bias derived from the randomization process:** it is carried out through the Office - Excel platform by means of algorithms for the generation of random numbers and their assignment to the specific group, by means of a simple impaired randomization; in order to maintain the masking of the assignment, a number (1-2) will be assigned to classify the intervention and its comparator, keeping this hidden from most researchers.
- **Bias due to deviations from planned interventions:** from study design, with simple randomization, the subject who has received a group assignment cannot move on to the other.
- **Bias due to the lack of outcome data:** The number of stratified lost data of intervened versus non-intervened will be evaluated, if it exceeds 5% analysis and data imputation will be made.

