According to the described methodology, the significance level for the primary objective is 0.05.

Procedure to Explain Missing Data

Any deviation from the statistical plan will be discussed with all authors for approval.

Selection of subjects to be included in the analyses

The final analysis will include all individuals with complete data.

Ethical considerations

The research group will submit to the Ethics Committee for consideration all required documentation from the study, explain the risks and benefits and ask for their written consent. Each participant shall have the right to leave the study when he/she so arranges. The study will follow the Good Clinical Practice regulations of the Helsinki Declaration. An adverse effects data collection sheet will be used, it is estimated that possible adverse effects will be related to taking capillary puncture for POCA1C (puncture site infection and pain or dizziness/vomiting).

Data management and record keeping

Data management and record keeping will be carried out in accordance with the current procedures of MetricsMed and a specific parameterization is contemplated for the implementation of this project.

Financing and insurance (budget and schedule of activities)

	
Effectiveness comparison of the hemoglobin measurement glycosylated at the point of care (POC-A1c), vs the standard current based on tolerance test oral to glucose, for the detection early of Diabetes Mellitus guy 2 (DM2) in Colombia. EDDIT-1 STUDY
	
Version: 3.0 Date: February 15, 2022

---	--	---

See annex budget 5.

Publication Policy

The publications will be based on data from the center, analyzed according to the protocol. Researchers undertake not to publish data obtained in a centre or in a small group of centers before the main publication (or updates of the same), unless they are formally accepted by all other researchers. Authorship, order of authors, publications and results of the study shall be determined in accordance with the authors according to international standards for publications.

[figure not shown]
Annexes

1. Flow of interventions and procedures
2. Informed consent
3. FINDRISC Questionnaire
4. Table of variables
5. Schedule of activities – Budget

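### Follow-up ends at any stated withdrawal, without separating refusal of calls from refusal of data use, so OGTT attendance can be lost from a complete-case primary analysis

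*Combined protocol and SAP*

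**What the plan says.** The section *Follow-up of withdrawn subjects* gives one unconditional rule: "Once the subject expresses his intention to withdraw, the follow-up will be terminated". The section before it, *Whether to replace subjects and how*, adds: "Withdrawn subjects will not be replaced". The heading above both announces the type and time of data collection for withdrawn subjects, but its text names no data item.

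Under *Setting the primary endpoint*, "the primary outcome is the probability of going to OGTT according to the strategy implemented". The OGTT may be done "in the CAIMED partner laboratory or in the laboratory of their choice" (*Study procedures*). Attendance is learned mainly from calls at 30 and 90 days and from a result that the participant sends in. There is a second route. *Instructions to the patient* puts the sequence number and the identification number on the order, so that the participant is recognised at the sampling site: "This will make it possible to monitor which participants have already completed the GGP" (GGP is evidently a translation variant of OGTT).

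On analysis, *Selection of subjects to be included in the analyses* states: "The final analysis will include all individuals with complete data". *Bias Control* has lost data compared by arm and says "if it exceeds 5% analysis and data imputation will be made". The section on missing data gives no handling rule. Nothing says whether a withdrawn participant counts as a non-attender.

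**The concern.** The flyer, the order and, in group A, the POC-A1c are all delivered at visit 1. What remains for the participant is the OGTT itself and the calls about it, so withdrawing largely means declining contact about the behaviour that the trial measures. It is plausible that such people attend less often. The synopsis describes a "Prospective, open label, randomized, controlled study", and only group A receives an A1c result, so it is also plausible that withdrawal differs by arm.

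If follow-up stops and only complete data are analysed, these people leave the denominator. The comparison of A with B then depends partly on who withdrew. Some of that loss is avoidable, because the order numbers provide a route to attendance that needs no call.

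**Working it through.** **Inputs from the documents** (*Sample size*, *Level of significance*): attendance 60% in A and 50% in B; power 80%; significance level 0.05; 392 per arm, then A raised by 30% to 510, total 902. Sidedness is not stated.

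**Assumptions, not in the documents:** w = share of an arm that withdraws with attendance unknown; q = share of those withdrawers who truly do not attend.

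**1. The plan's own figure.** The two-sided pooled formula gives

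n = [1.96·√(2·0.55·0.45) + 0.8416·√(0.60·0.40 + 0.50·0.50)]² / 0.10² = (1.379 + 0.589)² / 0.01 ≈ 388 per arm.

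With variance 0.25 in both arms it is (1.96 + 0.8416)²·0.50 / 0.01 = 392.4. The stated 392 is reproduced within rounding and choice of formula. Then 392 × 1.3 = 509.6, so 510, and 510 + 392 = 902. Power at 510/392 with everyone analysed is 85.1%. The 30% increase is for normal POC-A1c results; there is no allowance for withdrawal.

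**2. Complete-case rate in an arm with true rate p:** (p − w(1 − q)) / (1 − w). When q = 100% this is p / (1 − w).

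**3. Illustration with neither arm above 5%, q = 100%.**

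- 2% A, 5% B: 0.60/0.98 − 0.50/0.95 = 0.612 − 0.526 = 0.086.
- 5% A, 2% B: 0.60/0.95 − 0.50/0.98 = 0.632 − 0.510 = 0.121.
- No true effect (50% in both arms): 0.50/0.95 − 0.50/0.98 = 0.526 − 0.510 = 0.016, in favour of the arm with more withdrawals.

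The first pattern involves 510 × 0.02 + 392 × 0.05 = 29.8 people (3.3% of 902); the second 510 × 0.05 + 392 × 0.02 = 33.3 (3.7%).

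**4. Rejection probability** (normal approximation, two-sided 0.05, on the numbers left after withdrawal):

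| Withdrawn A / B | q | Rate A | Rate B | Difference (points) | Power | Rejection if 50% v 50% |
|---|---|---|---|---|---|---|
| 0% / 0% | – | 60.0% | 50.0% | 10.0 | 85% | 5.0% |
| 5% / 5% | 100% | 63.2% | 52.6% | 10.5 | 87% | 5.0% |
| 2% / 5% | 100% | 61.2% | 52.6% | 8.6 | 72% | 7.6% |
| 5% / 2% | 100% | 63.2% | 51.0% | 12.1 | 95% | 7.6% |
| 2% / 5% | 80% | 60.8% | 51.6% | 9.2 | 78% | 5.9% |
| 5% / 2% | 80% | 62.1% | 50.6% | 11.5 | 93% | 5.9% |

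**5. The 5% trigger.** It is not said whether 5% is per arm or overall. With 2% in A and 8% in B, the overall loss is (10.2 + 31.4)/902 = 4.6%. An overall trigger would not be reached, yet the complete-case difference is 0.60/0.98 − 0.50/0.92 = 6.9 points, with power 52%.

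**6. Check of the remedy.** If everyone randomised stays in the denominator and undocumented withdrawers are classed as non-attenders, the rate is p − w(1 − q). At q = 100% this returns 60% v 50%. At q = 80%, 2%/5% gives 59.6% − 49.0% = 10.6 points and 5%/2% gives 59.0% − 49.6% = 9.4 points, each 0.6 from the truth; complete cases miss by 0.8 and 1.5. If withdrawers attend as often as others in their arm, complete cases are right, and classing gives 0.60·0.98 − 0.50·0.95 = 11.3 points or 0.60·0.95 − 0.50·0.98 = 8.0 points. The classing rule is therefore also an assumption and needs a sensitivity analysis.

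**The case against.** The strongest reply has four parts.

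- **Imputation is planned.** *Bias Control* provides for it above 5%. This stands as a partial safeguard, and larger illustrations must respect it. For example, 8% in A and 3% in B would give 13.7 points on complete cases, but that is 52.6/902 = 5.8% overall and crosses the trigger on either reading. The safeguard is weak: no method is given, it does nothing at or below 5%, it cannot recover attendance never collected, and it conflicts with the complete-data analysis set.
- **The harm comes from the analysis set.** Keeping all randomised participants and classing undocumented attendance as non-attendance would remove the distortion when no withdrawer attends, with the withdrawal rule unchanged. This is right as far as it goes: the two rules do harm together, and the fix must address both.
- **The laboratory route is limited.** Any laboratory is allowed, so absence from the allied laboratory's list does not prove non-attendance. This stands. The share of OGTTs done elsewhere is not given.
- **The follow-up that ends may mean only the calls.** The protocol often uses the word that way, and nothing says that laboratory monitoring stops or that data already held are discarded. The wording allows this reading but does not settle it.

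The consent form is not available here, so it may already separate levels of withdrawal or permit a laboratory look-up. Non-replacement is ordinary in a randomised trial and is not a fault. Failure to reach someone by telephone is a different problem, which this rule does not govern.

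**Conclusion.** The point holds as a gap in the withdrawal rule that acts together with the complete-case set. An undifferentiated stop can drop withdrawers from the primary endpoint when part of the information could still be obtained without contact.

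Its size cannot be fixed from the documents. In the illustration with at most 5% lost in either arm and all withdrawers non-attenders, the 10-point difference moves to between 8.6 and 12.1, and rejection under no effect rises from 5% to about 7.6%. With 80% non-attenders, the range is 9.2 to 11.5 and the rejection probability 5.9%. Equal withdrawal with the same q in both arms inflates both rates but leaves type I error at 5%.

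A reader might infer that withdrawers are known to be non-attenders, that withdrawal will be unequal, or that the result will lean towards group A. The documents support none of these; both are plausible mechanisms without a figure, and the direction is open. A reader might also infer that every withdrawer's outcome is necessarily lost. An OGTT documented before withdrawal need not be lost, and the laboratory route is not expressly closed. Nor does this show the sample size to be wrong. The change is worth making because it is cheap and protects the primary outcome.

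**What to change.** 1. **Define two levels of withdrawal** in *Follow-up of withdrawn subjects*. Withdrawal from calls: no further contact; data already collected are kept; where consent allows, OGTT attendance and date are still read from the allied laboratory by tracking number to day 90. Withdrawal of consent for data use: collection stops. Check that the consent form matches, and amend it if it does not.
2. **State the analysis rule.** Keep participants who only decline calls in the randomised denominator. In the primary analysis, class those with no documented OGTT by day 90 as non-attenders. Add a sensitivity analysis that varies this assumption separately by arm.
3. **Record and reconcile.** Record level, date and reason of withdrawal by arm. Reconcile the imputation rule in *Bias Control* with the complete-data set: say whether 5% is per arm or overall, which method is used, and which rule governs.

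The cost is a protocol paragraph, short additions to the analysis plan, a consent check, a few database fields and one extra analysis, with no new visit or test. The downside is that OGTTs done in another laboratory by people who refuse calls stay unseen and would be classed as non-attendance. The sensitivity analysis is there to show how much that matters.

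### Allocation concealment from enrolling staff is not assured: the arm code is hidden only from most researchers, and nothing requires eligibility to be locked before the arm is shown

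*Combined protocol and SAP*

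**What the plan says.** Four places in the combined protocol and SAP bear on this.

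- **Bias Control, randomization item.** On the source of the sequence: "it is carried out through the Office - Excel platform by means of algorithms for the generation of random numbers". Randomization is simple. For the stated purpose, "in order to maintain the masking of the assignment", the measure is that "a number (1-2) will be assigned to classify the intervention and its comparator", "keeping this hidden from most researchers".
- **Allocation of the intervention.** After consent, the doctor verifies FINDRISC and the eligibility criteria, and "random assignment will be carried out by the research team". On the source of the sequence: "The random allocation sequence will be automatically generated through the platform intended for this purpose". A team member then records the group on the data platform.
- **Scheduling of study visits, Visit 1.** The doctor obtains consent and reviews eligibility. A separate row gives the research assistant "VERIFICATION of FINDRISC, Randomization and data processing on the platform".
- **Type of design; Setting the primary endpoint.** The trial is open label, and the primary outcome is whether the participant goes for the OGTT.

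The text available names no custodian of the sequence, no sealed or locked list, no independent allocation service, and no step that registers a participant irreversibly before the arm is revealed. The flow figure in Annex 1 is not reproduced, so it could not be checked.

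**The concern.** Concealment protects a trial only if nobody who decides on entry can know the next assignment. A promise that covers most researchers leaves an unnamed remainder. The plan does not say whether that remainder is one list holder with no contact with participants, or includes the doctor or research assistant at the screening site.

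The endpoint makes this matter. Attendance for a fasting laboratory test is a behaviour that a recruiter can partly judge from conversation. Someone who knew the next arm could delay or decline a participant, or re-score a FINDRISC value near 12. The resulting imbalance would fall directly on the only primary comparison. It could not reliably be adjusted away, because the variables in Annex 4 include no measure of motivation to attend.

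**Working it through.** **1. The passages side by side**

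| Question | Allocation of the intervention | Bias Control / visit table |
|---|---|---|
| Source of the sequence | Unnamed platform, automatic | Office-Excel random numbers |
| Who verifies FINDRISC | The doctor | The research assistant, who also randomises |
| Who assigns | The research team | The research assistant |
| Hidden from whom | Not stated | Most researchers |
| Eligibility locked before the arm is shown | Not stated | Not stated |

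Automatic generation describes how a sequence is made, not who can see it. Placing randomisation after consent and the eligibility check gives an order of steps. Without a lock it does not prevent someone with access to the sequence from acting on it.

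**2. The plan's own sample size**

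Inputs from the Sample size and Level of significance sections: 50% versus 60%, 80% power, alpha 0.05 (two-sided, as the 95% interval implies).

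- Pooled normal formula, no continuity correction: 388 per arm, within about 1% of the stated 392.
- Variance fixed at 0.25 in both arms: (1.960 + 0.842)² × (0.25 + 0.25) / 0.10² = 7.849 × 0.5 / 0.01 = 392.4, which matches 392.
- Group A increased by 30%: 392 × 1.3 = 509.6, giving 510, and 510 + 392 = 902.

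The sample size reproduces, and this point does not change it.

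**3. Illustration of what selection could do**

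From the plan: arms of 510 and 392, and attendance of 50%. Assumed, with no source in the documents: a share s of the places in each arm is exchanged between likely and unlikely attenders, the two classes differ by g in attendance, and every exchange favours A.

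Shift in the difference = 2 × s × g:

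| s | g | Shift |
|---|---|---|
| 2% | 20 points | 0.8 points |
| 2% | 40 points (70% vs 30%) | 1.6 points |
| 5% | 20 points | 2.0 points |
| 5% | 40 points | 4.0 points |

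With unequal arms the same share is not the same count: 2% is about 10 places in A and 8 in B. The shifts are therefore approximate.

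Standard error with no true effect = √[0.25 × (1/510 + 1/392)] = 0.0336. The two-sided rejection probability for a shift b is approximately Φ(b/0.0336 − 1.96) + Φ(−b/0.0336 − 1.96):

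| Shift b | b / SE | False-positive rate |
|---|---|---|
| 0 | 0 | 5.0% |
| 0.8 points | 0.24 | 5.7% |
| 1.6 points | 0.48 | 7.6% |
| 2.0 points | 0.60 | 9.1% |
| 4.0 points | 1.19 | 22.2% |

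**The case against.** The strongest reply is that this is a gap in description and not a stated defect. The plan declares an intention to mask the assignment, generates the sequence automatically, and randomises after consent and the eligibility check. Someone must hold any sequence, so a code hidden from most researchers is literally compatible with sound practice. The hidden item is most directly the 1-2 code, not a list. This stands: a reader might infer that allocation is not concealed, or that recruiters hold the list, and the documents say neither.

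A reader might also infer that one research assistant both decides eligibility and randomises. The visit table gives that role the FINDRISC verification, but the Allocation section gives it to the doctor, and the table itself leaves the eligibility review with the doctor. What the documents support is a contradiction. Re-scoring would also be harder than it sounds, because FINDRISC was already applied at pre-screening.

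Nor does the open label by itself create the risk. Under simple randomisation, past arms do not predict the next one. The exposure comes from access to the sequence or code key, or from repeating a draw.

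The reply does not remove the gap. If only the 1-2 code is hidden, the plan says nothing about hiding the sequence. A two-value code is also broken once one coded participant is seen to receive POC-A1c.

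**Conclusion.** The point holds in this form: concealment from enrolling staff is not assured. The written rule covers only most researchers, the source of the sequence is described in two ways, no lock precedes release of the arm, and the FINDRISC verifier is inconsistent. That is enough to call for a change, because the rule is weaker than concealment from everyone who enrols.

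The documents do not support saying that selection has occurred or will occur. The range of about 6% to 22% is illustrative only. It rests on assumed exchange shares of 2% to 5%, assumed attendance gaps of 20 to 40 points, and steering that always favours group A. Weaker prediction or less consistent steering gives smaller shifts, and with no steering the rate stays at 5%.

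**What to change.** In Bias Control, replace the clause on hiding the code from most researchers with a rule along these lines: *The allocation sequence and the code key are generated and held by a person with no role in recruitment. They are hidden from everyone who obtains consent, scores FINDRISC, checks eligibility or enrols. One assignment is released at a time, only after consent, the verified FINDRISC score and all eligibility items have been saved and the participant irreversibly registered.*

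Also:

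- State one source for the sequence, reconciling the platform in the Allocation section with Office-Excel in Bias Control.
- State one role for FINDRISC verification, reconciling the Allocation section with the visit table, and require it to be complete before randomisation.

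The cost is protocol wording and a small set-up step before recruitment. Sample size and visits are unchanged. The sponsor must confirm that the data-management function can hold the list and release assignments in this way. The Data management section refers only to existing procedures and a project-specific set-up, and does not say so.
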